Methodology	Multi-centre, two-arm randomised controlled trial with nested qualitative exploration of participant and physiotherapist views
Sponsor name	King's College London/Guy's & St Thomas Foundation NHS Hospital
Chief Investigator	[name]
REC number	17/LO/0568
Medical condition or disease under investigation	Peripheral Arterial Disease (PAD)
Purpose of clinical trial	Phase II efficacy trial
Primary objective	To answer the question "Does MOSAIC improve walking ability (measured by the 6 Minute Walking Distance [6MWD]) at 3 months compared to usual NHS care in older people with intermittent claudication (IC)?"
Secondary objective (s)	To answer the questions 1) "Does MOSAIC improve a) activities of daily living and quality of life [QoL] at 3 months; and b) walking ability, activities of daily living and QoL at 6 months compared to usual NHS care in people with IC?" 2) "Is it feasible to collect the measures required to estimate cost utility in future phase 3 trials in people with IC?" 3) What are the Minimal Clinically Important Difference (MCID) values for the clinical assessments used for people with IC?
Number of Subjects/Patients	192
Trial Design	Phase II, multi-centre, parallel group, two-arm, randomised, controlled superiority trial

	Drimony and points 2 month post intervention accordent
Endpoints	Primary endpoint: 3 month post-intervention, secondary
	endpoint: 6 months post randomisation.
Main Inclusion Criteria	 Inclusion criteria: a) ≥50 years of age; b) established PAD (Ankle Brachial Pressure Index ≤0.90 and/or radiographic evidence or clinician reported diagnosis) and IC (presence of symptoms reported on the San Diego Claudication Questionnaire (SDCQ)); c) able to participate in MOSAIC and d) able and willing to provide informed consent. Exclusion criteria: a) Unstable IC (self-reported change in symptoms during previous 3 months); b) walking >90 minutes/week (reported on Brief International Physical Activity Questionnaire (IPAQ)); c) contraindications to walking exercise (e.g., unstable angina) confirmed by their vascular specialist; or d) have completed any prescribed supervised exercise sessions in the previous 6 months or been offered prescribed exercise
	sessions in the next 6 months.
Statistical Methodology and Analysis	The analysis will be conducted according to the intention to treat. The primary outcome will be analysed using multiple regression with the baseline 6MWD value and the stratification factor, centre, included as covariates. Results will be reported as the difference in mean 6MWD between the intervention and control groups with a 95% confidence interval (CI). Other continuous outcomes will be similarly analysed. Logistic regression will be used to analyse binary outcomes, with the models including the stratification factor, centre, as a covariate. The sensitivity and consistency of the EQ-5D-5L will be analysed using correlations with VascuQoL-6 and other clinical measures. Feasibility of collecting service use data using an adapted version of the CSRI will be assessed. A small number of participants (N=20) will be invited to complete the scale with a researcher and describe their thoughts whilst completing it to ensure it is clear and appropriate. A short rating scale will be added to scales at follow up to allow the calculation of Minimal Clinically Important Differences (MCID).

Glossary of Terms and Abbreviations

6MWD	6 minute walking distance
6MWT	6 minute walking test
AE	Adverse Event
ANOVA	Analysis of Variance
AR	Adverse Reaction
ASR	Annual Safety Report
Brief IPQ	Brief Illness Perception Questionnaire
CA	Competent Authority
CI	Chief Investigator
CRF	Case Report Form
CRN	Comprehensive Research Networks
CRO	Contract Research Organisation
DMC	Data Monitoring Committee
EARS	Exercise Adherence Rating Scale
EC	European Commission
EQ-5D-5L	EuroQoL- 5 Dimension -5 Level
GAfREC	Governance Arrangements for NHS Research Ethics Committees
IC	Intermittent Claudication
ICF	Informed Consent Form
IPAQ	Brief International Physical Activity Questionnaire
ISRCTN	International Standard Randomised Controlled Trial Number
MA	Marketing Authorisation
MCID	Minimal Clinically Important Difference
MRC	Medical Research Council
MS	Member State
Main REC	Main Research Ethics Committee
NEADL	Nottingham Extended Activities of Daily Living
NICE	National Institute for Health and Care Excellence
NHS R&D	National Health Service Research & Development
PAD	Peripheral Arterial Disease
Participant	An individual who takes part in a clinical trial
PI	Principal Investigator
QA	Quality Assurance
QALYs	Quality Adjusted Life Years
QC	Quality Control
QoL	Quality of Life
RA	Research Associate
ROC curve	Receiver Operating Characteristic Curve
RCT	Randomised Controlled Trial
REC	Research Ethics Committee
SAE	Serious Adverse Event

SDCQ	San Diego Claudication Questionnaire
SDV	Source Document Verification
SEM	Standard error of the mean
SOP	Standard Operating Procedure
SR-MWD	Self-Reported Maximum Walking Distance
SSA	Site Specific Assessment
TASC	Trans-Atlantic Inter-Society Consensus
TMG	Trial Management Group
TPBQ	Theory of Planned Behaviour Questionnaire
TSC	Trial Steering Committee
VascuQol-6	Vascular Quality of Life Questionnaire
WELCH	Walking Estimated-Limitation Calculated by History

1. Introduction

Intermittent claudication (IC) is a severe ischaemic leg pain which occurs during walking in ~30% of people with Peripheral Arterial Disease (PAD), an age-related atherosclerotic condition [Wang et al., 2005]. It results in reduced mobility, participation in daily activities [Treat-Jacobson et al, 2002], quality of life (QoL) [Pell, 1995; Regensteiner et al, 2008] and feelings of powerlessness, inadequacy and isolation [Treat-Jacobson et al, 2002, Gibson et al, 1998]. Walking is an effective treatment for IC [Vemulapalli et al, 2015], improving walking distances and duration compared to usual NHS treatment [Lane et al, 2014] or pharmaceutical therapy [Ahimastos et al, 2011] and with comparable outcomes to revascularisation [Murphy et al, 2012; 2015]. The Trans-Atlantic Inter-Society Consensus (TASC)-II Group recommends supervised walking at an intensity that induces pain within 3–5 minutes, for 30–60 minutes/session conducted 3 times/week for 3 months [Norgren et al, 2007]. Similarly, the National Institute for Health and Care Excellence (NICE) recommends 2 hours supervised exercise/week for 3 months [NICE 2012]. However, guideline implementation is poor [NICE 2014] and only 24% of UK vascular surgeons have access to supervised walking programmes [Stewart & Lamont, 2007], so usual care for most individuals with IC is simple advice to "go home and walk" [Stewart & Lamont, 2007; Makris et al, 2012]. Despite advice, self-directed walking is frequently overlooked as a management strategy [Galea [name] et al 2015] and participation is low [Garg et al, 2006, Galea et al, 2008], leading to reduced mobility and a need for higher-risk invasive treatments.

There are unique barriers to walking among people with IC [Galea et al, 2008], as walking is both a stimulus for pain and a therapy, which makes walking counterintuitive without appropriate guidance and support. Our previous work identified modifiable psychosocial factors, such as people's understanding of IC, perceptions of and confidence in their ability to manage IC [Galea [name] et al, 2015a; 2015b], and unrealistic expectations of treatment as key factors influencing walking [Galea [name] et al, 2015]. Evidence from our recent systematic review, including 6 randomised controlled trials (RCT), suggests that targeting these psychological barriers using behaviour-change techniques (e.g., using motivational interviewing to elicit patient values and desire for change) in addition to exercise or advice may increase walking in people with IC [Galea et al, 2013].

Two psychological models which we applied to change health behaviour are the Theory of Planned Behaviour [Ajzen 1985; 1991] and Common Sense Model of Illness Representations [Leventhal et al, 1980; Leventhal et al, 1984]. The Theory of Planned Behaviour proposes that behaviour (e.g., walking) is goal-directed and driven by beliefs about social (e.g., approval from a healthcare professional), personal (e.g. confidence to engage in walking), and environmental factors (e.g., perceived access to a safe walking route) [Ajzen 1985; 1991]. The Common Sense Model proposes that individuals form personal, lay explanations of their illness, which reinforce maladaptive coping behaviours (e.g., avoid painful walking) or drive change (e.g., increase walking to improve symptoms), and that inaccurate or limited understanding of their illness and treatment may prevent healthy behaviour change [Leventhal et al, 1980; Leventhal et al, 1984]. Our work was the first to combine processes from these two theories to target walking behaviour change among people with IC.

Consistent with MRC guidelines for developing complex healthcare interventions, we worked with people with IC and clinicians to co-design and test the feasibility of a novel physiotherapist-led behaviour-change intervention (2 face to face sessions and 2 follow-up telephone sessions over 3 months) to increase walking in people with IC. The feasibility study (n=24) was successful: We enrolled 39% of identified patients, study retention was good (92%), compliance with the intervention was high (100% meetings and 87% phone calls), 86% of participants completed all outcome measures and a subsample of participants and the physiotherapist reported the study was a positive and acceptable experience during qualitative interviews [Galea [name] et al, 2015]. The feasibility study was not designed to estimate the effect of our intervention on walking ability but did show that walking increased by mean (SD) 837 (626) steps/day. We refined the intervention in response to participant feedback (e.g. provision of a pedometer).

This study will build on our previous work to investigate the efficacy of our brief physiotherapist-led behaviour change intervention (**Mo**tivating **S**tructured walking **A**ctivity in people with Intermittent **C**laudication – MOSAIC) on walking ability compared to usual care in older people with IC in a RCT.

2 Trial Objectives, Design and Statistics

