Walking Estimated-Limitation Calculated by History (WELCH) is a 4 item measure of walking limitation in patients with IC (Ouedraogo et al, 2013; Tew et al., 2014). Scores range from 0-100, with 0 indicating ability to walk for 30 seconds slowly and usually slower than others of the same age and 100 indicating ability to walk \geq 3 hours quickly and usually faster than others of the same age.

Nottingham Extended Activities of Daily Living (NEADL) (Nouri & Lincoln, 1987; Lincoln & Gladman, 1992) scale is a 22 item measure with 4 subscales (mobility, kitchen tasks, domestic tasks, leisure activities). Each item is scored 0-3 with a total score ranging from 0-66.

Vascular Quality of Life Questionnaire-6 (VascuQol-6) is a disease specific measure comprising 6 items (each scored 1-4; total score, 6-24) (Nordanstig et al, 2014).

Brief International Physical Activity Questionnaire (IPAQ) (Craig et al., 2003) is a valid and reliable 7-item measure of daily physical activity. The self-administered short form asks participants to recall the frequency (days) and duration (minutes) of moderate and vigorous activities, walking for \geq 10 minute bouts, and sitting over the last 7 days.

Post intervention (3 month) visit:

6 Minute Walking Distance (6MWD), Self-reported maximum walking distance (SR-MWD), Walking estimated-limitation calculated by history (WELCH), Nottingham extended activities of daily living (NEADL) Vascular quality of life questionnaire (VascuQol-6) Brief International Physical Activity Questionnaire (IPAQ)

Adverse events - the response to a single open ended item "Have you had any problems since your last assessment?" will be recorded (please see section 6)

6 month postal pack:

Self-reported maximum walking distance (SR-MWD), Walking estimated-limitation calculated by history (WELCH), Nottingham extended activities of daily living (NEADL) Vascular quality of life questionnaire (VascuQol-6) Brief International Physical Activity Questionnaire (IPAQ) Adverse events- the response to a single open ended item "Have you had any problems since your last assessment?" will be recorded

If the participant does not return the postal questionnaires despite two reminders the researcher will telephone the participant to collect the minimum data set (Adverse events, SR-MWD, IPAQ, VascuQoL-6)

B: Cost effectiveness assessment

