The feasibility of collecting measures to estimate the economic impact (cost effectiveness analysis) of our intervention in future definitive Phase 3 trials will be assessed. The EQ-5D-5L, which provides utility weights to generate Quality Adjusted Life Years (QALYs), will be administered at all time points and compared against the VascuQoL-6 and other clinical outcomes. EQ-5D-5L evaluates five dimensions (self-care, mobility, usual activities, pain/discomfort and anxiety/depression; score, 0-5).

A resource use questionnaire will be developed based on previous work (e.g. Client Service Receipt Inventory) to identify key cost drivers (both NHS and non NHS) and evaluated at all time points to determine completion rates, redundant questions and additional resource use items. To qualitatively evaluate understanding, recall and scale completion, a sub sample of participants (up to n~20) will be invited to complete the questionnaire whilst describing their thoughts. If needed, the researcher will ask probe questions (e.g. what do you think this question is asking you? Is the question confusing? If so, what would make it easier to answer? How did you arrive at your answer? What does the word/phrase ____ mean to you?) The sessions will be audio-recorded and transcribed verbatim, following which recordings will be destroyed. The transcripts from separate questions will be coded thematically (informed by content analysis) to identify the type and degree of difficulty the participants expressed with answering it (French 2007). Identified patterns will be reviewed by the research team and the final scale amended to maximise understanding and usability.

C: Process evaluation

Informed by guidelines, the implementation of MOSAIC (e.g., adoption at sites, characteristics of trial physiotherapists, intervention attendance and adherence, context of treatment delivery), maintenance (at 6 months), unexpected pathways and consequences (referral to and

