4.3 Visit windows

The MOSAIC intervention visit windows are weeks: 1, 2, 6 and 12.

Both groups are assessed at week 0 (baseline), week 12 (3 months) and week 24 (6 months) follow up.

5 Data collection

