10.1 General Methodology

All analyses will not be carried out unless the trial database has been authorised as complete and final, and all protocol deviations have been identified.

The analyses will be performed by the trial statistician and the primary analysis will be reviewed by a second statistician. ITT will be the main strategy of analysis adopted for the primary outcome and the secondary outcomes 1a; 1b and 3. Also, all regression analysis will include the stratification factor, centre, as a covariate.

Continuous data will be summarised in tables using descriptive statistics, including the number of participants, mean, standard deviation, median and range as appropriate. Summaries of continuous characteristics will be based on non-missing observations. For categorical variables, counts and percentage per treatment group will be presented. Percentage for categorical variables will be calculated based on number of patients with non-missing values for the variable. Range checks of the data will be performed to identify anomalous values.

All statistical hypothesis testing will be done using two-sided tests with type I error of 0.05, unless otherwise stated.

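### Nothing planned for objective 2 shows how many randomised participants have both a computable QALY and a computable cost

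*Protocol*

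**What the plan says.** Objective 2 appears in the Protocol synopsis, Protocol 2.1 and SAP 6.2: "Is it feasible to collect the measures required to estimate cost utility in future phase 3 trials in people with IC". Two instruments serve it.

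- **Resource use.** The synopsis says "Feasibility of collecting service use data using an adapted version of the CSRI will be assessed". Protocol 4.4 B has the form "evaluated at all time points to determine completion rates, redundant questions and additional resource use items". It also plans to identify the main cost drivers, and to run think-aloud sessions with up to about 20 people, after which the form is amended.
- **EQ-5D-5L.** Protocol 4.4 B says it supplies the utilities for QALYs and "will be administered at all time points and compared against the VascuQoL-6 and other clinical outcomes". The synopsis and Protocol 2.4 add: "The sensitivity and consistency of the EQ-5D-5L will be analysed using correlations with VascuQoL-6 and other clinical measures". No completion rate is planned for it.
- **SAP.** Sections 5.3.3 and 5.3.4 list neither instrument, section 7 has no endpoint for objective 2, and sections 10.6 and 11 contain no analysis of it. Section 10.1 reads: "ITT will be the main strategy of analysis adopted for the primary outcome and the secondary outcomes 1a; 1b and 3".
- **Timing.** SAP 4.3: "Both groups are assessed at week 0 (baseline), week 12 (3 months) and week 24 (6 months) follow up".
- **6-month fallback.** Under Protocol 4.4 A, someone who has not returned the postal pack after two reminders is telephoned "to collect the minimum data set (Adverse events, SR-MWD, IPAQ, VascuQoL-6". Neither EQ-5D-5L nor resource use is on that list.

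**The concern.** A cost-utility estimate needs a cost and a QALY in the same person. Over this follow-up, that means an EQ-5D-5L index at baseline, 3 and 6 months, and usable resource use at 3 and 6 months. The plan describes each instrument separately and only one of them in terms of collection. A correlation between EQ-5D-5L and VascuQoL-6 is computed in people who completed both, so it can be high however many EQ-5D-5L forms are missing. A completion rate for one form at one time point cannot be lower than the proportion with all forms usable, given the same denominator.

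The SAP's default summaries do not close the gap. Section 10.1 bases continuous summaries and percentages on non-missing values, so people without the form leave the denominator.

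At stake is the planning figure passed to a phase 3 trial. The primary result is not affected.

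**Working it through.** **Inputs from the documents**
- 192 randomised, 20% attrition at 3 months for 6MWD (Protocol 3, SAP 8).
- Feasibility study, n=24: 92% retained, 86% completed all outcome measures (Protocol 1).

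**Not in the documents, so assumed**
- Both baseline forms complete.
- The same 80% followed at 3 and 6 months.
- Each form usable in a proportion c of those followed, with c from 0.86 to 0.95.
- Dependence between omissions anywhere from independent to fully nested (the same people omit every form).

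**1. The plan's own figure.** Per arm: 2 × [111 × (1.960 + 1.282) / 58]² = 76.97. Total with attrition: 2 × 76.97 / 0.80 = 192.4, which agrees with 192. That is the denominator used below.

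**2. Reading the 86%.** It counts participants who completed everything, so it is already a joint rate. 92% of 24 is 22 people. 19/22 = 86.4% fits, while 20/24 = 83.3% and 21/24 = 87.5% do not. It is therefore probably a rate among those retained; this is an inference, since no counts are given. On that reading the joint share is 0.80 × 0.86 = 0.69, or 0.92 × 0.86 = 0.79 with the feasibility study's retention.

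**3. Illustration by form.** Four follow-up forms are needed: two instruments at two time points. Per-form share = 0.80 × c. Joint share = 0.80 × c⁴ if omissions are independent, and 0.80 × c if fully nested.

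| c | Per form, of those randomised | Joint, independent | Joint, nested | Gap below the per-form rate |
|---|---|---|---|---|
| 0.86 | 69% | 44% | 69% | 0 to 25 points |
| 0.90 | 72% | 52% | 72% | 0 to 20 points |
| 0.95 | 76% | 65% | 76% | 0 to 11 points |

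**4. Other follow-up levels.** No 6-month attrition is stated. With 70% followed at 6 months, all of them also seen at 3 months, the independent case is 0.70 × c⁴ = 38% to 57%. With 92% at both, it is 0.92 × c⁴ = 50% to 75%.

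**5. Telephone-only contacts.** Each such participant is reached at 6 months but has neither instrument then. Each lowers the highest attainable joint share by 1/192 = 0.5 points. Their expected number is not given.

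**6. Precision.** Half-width = 1.96 × √[p(1 − p)/192] = 7.0 points at p = 0.44 and 6.0 at p = 0.76. With 96 per arm it is 9.9 and 8.5.

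**The case against.** **Clustering.** Both instruments come at the same visit or in the same pack, so omissions probably cluster and the joint share may lie close to the per-form rate. This is a fair point. A reader might infer that only about half the participants will have a cost and a QALY. The documents do not support that: it needs near-independent omissions and treats the 86%, already a joint figure, as a rate per form.

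**Attrition.** The 20% was set for the walking test, and Protocol 4.4 A lets people who cannot attend at 3 months complete secondary outcomes at home. Questionnaire loss may be smaller. This stands, and it is why 80% is only an assumption.

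**Other feasibility work.** A reader might say that feasibility rests on completion rates alone. Protocol 4.4 B also plans work on cost drivers, item review and think-aloud sessions. These test the content and clarity of the resource-use form, not joint completeness.

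**No decision rule.** Neither document sets a threshold, so the plan does not commit anyone to declaring feasibility on a per-form rate. Nor has objective 2 been dropped: SAP 6.2 restates it, and the Protocol's analyses still apply.

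**Think-aloud forms.** A reader might infer that researcher-assisted forms inflate the completion rate. The documents do not say these forms count towards it. If 20 fully complete ones all fell at one time point among 154 returned (0.80 × 192), the gain would be 20(1 − p)/154, or 2.6 to 5.2 points for an unaided rate p of 0.80 to 0.60. Spread over three time points, about 7 each, it would be 0.9 to 1.8 points.

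**Incomplete cases.** Phase 3 could use imputation or longitudinal models, so participants with some forms missing need not be excluded. This stands. The joint share counts people with complete data and does not limit who can be analysed.

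**Conclusion.** The reporting gap holds on the text alone. Objective 2 has no SAP analysis, EQ-5D-5L has no planned completion rate, and nothing defines completeness of both instruments in the same person. The telephone fallback leaves both instruments missing at 6 months for anyone reached only that way.

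The size is unknown. With 80% followed at both time points and complete baseline data, the joint share is about 69% if the feasibility study's 86% carries over as a joint rate. That study had 24 participants, and the Protocol does not say whether its measures included these two. The illustrative range is 44-65% under independence and 69-76% if fully nested, so the joint figure could equal the per-form rate or lie up to 25 points below it. Measuring it resolves that uncertainty. This is a worthwhile, inexpensive correction to a descriptive secondary objective.

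**What to change.** Add an objective 2 analysis to the SAP, by arm and overall, with all randomised participants as denominator and 95% CIs:

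1. the proportion with an EQ-5D-5L index computable at baseline, 3 and 6 months;
2. the proportion with usable resource use at 3 and 6 months;
3. the proportion with both.

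Make the third the main summary for objective 2. Report it alongside the completion rates per form and per time point, not in place of them, because those rates show which instrument fails and when. Count telephone-only 6-month contacts as missing for both instruments. If any think-aloud form also serves as a trial form, show it separately from unaided completion.

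The cost is some SAP wording and one extra table from data the Protocol already plans to collect. The downside is a headline figure that may be lower, and cannot be higher, than the per-form rates on the same denominator.
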